**Suppression of Phoenixin-14 Predicts Mortality in Sepsis: Evidence from
Serum Levels and Gene Expression**

[name] [name]

30.04.2025

Department of Anesthesiology and Reanimation, Firat University Medicine Faculty Hospital,
Elazig 23300, Turkey

Study Protocol

Study Design and Patients

In this prospective observational cohort study, patients aged 18 years and older admitted to our tertiary intensive care unit with diagnoses of sepsis and/or septic shock were evaluated. Ethical approval was obtained from the Firat University Non-Interventional Research Ethics Committee on March 27, 2024, with the number 23376. The entire study was funded by the Firat University Scientific Research Projects Coordination Unit (FUBAP), under project number TF.24.11. Our study adhered to the Helsinki Declaration and the Strengthening the Reporting of Observational Studies in Epidemiology (STROBE) guidelines.

The treatment protocol for patients was followed according to the Sepsis-3 guidelines (1), and antibiotic therapy was administered in consultation with an infectious disease specialist, aiming at the source of sepsis. Septic shock was also defined according to the Sepsis-3 guidelines (1), based on the requirement for vasopressor support to maintain adequate mean arterial pressure despite adequate fluid resuscitation.

Patients under the age of 18, patients who were discharged/transferred or died within 72 hours after being diagnosed with sepsis, patients/relatives who refused to participate in the study, pregnant women, patients using chronic steroids, patients whose blood samples were collected

under inappropriate conditions, and patients with a history of malignancy or immunosuppression were also excluded from the study.

The study was started with participants who agreed after signing an informed consent form.

Collection of Blood Samples and Data

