GAPDH	5'-GAA GGT GAA GGT CGG AGT C-3'	5'-GAA GAT GGT GAT GGG ATT TC-3'
PNX-14	5'-CGG CTT CAT CTC CCT GAT CG -3'	5'ACA GCC CTC TCA TTT CCT GC-3'

GAPDH (glyceraldehyde-3-phosphate dehydrogenase; PNX-14: Phoenixin14

ELISA Protocol

Serum levels of Phoenixin-14 and cytokines were measured using commercially available ELISA kits (BT Lab, Shanghai, China) according to the manufacturer's instructions.

End points

Primary endpoint: the relationship between PNX14 levels and in-hospital mortality in patients with sepsis or septic shock. Secondary endpoints: to evaluate the tendency of PNX-14 levels to be suppressed at the molecular level in patients with sepsis and their potential as a translational biomarker. Additionally, to assess the relationship between PNX14 and SOFA scores, APACHE II scores, septic shock, requirements for mechanical ventilation or renal replacement therapy, and ICU length of stay in patients with sepsis. The correlation between PNX14 levels and those of CRP, procalcitonin, IL-1 β , IL-6, IL-10, and TNF- α was also examined as part of the endpoints.

Statistical Analysis

Before the study, calculations were conducted using G*Power 3.1 with 80% power, $\alpha = 0.05$, and an expected medium effect size ($d = 0.5$), indicating that at least 64 patients were needed. This requirement was met by including 77 patients in the study.

The data were analyzed using IBM SPSS Statistics for macOS, version 29.0 (IBM Corp., Armonk, NY, USA). Descriptive statistics for continuous variables are presented as mean \pm standard deviation for normally distributed data and median (Q1–Q3) for non-normal data; categorical variables are shown as frequency (percentage). Group comparisons between developing and non-developing patients were conducted with the independent samples t-test for normally distributed continuous data and the Mann–Whitney U test for non-normal data. Normality of continuous variables was checked with the Kolmogorov–Smirnov test. For categorical variables, either the Pearson chi-square test or Fisher's exact test was used, as appropriate.

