The relative quantification (RQ, $2^{-\Delta\Delta Ct}$) values from qPCR experiments were compared between two groups (Dead and Survived). The distribution of both groups was assessed using the Shapiro–Wilk test prior to analysis, and the assumption of normality was not rejected (D group $p=0.12$; S group $p=0.17$). Homogeneity of variances was evaluated with the Levene test, which indicated unequal variances ($p=0.018$). Therefore, the differences between groups were analyzed using the Welch independent samples t-test. Additionally, the nonparametric Mann–Whitney U test was performed to verify robustness.

The ability of each biomarker to predict mortality was evaluated using ROC (receiver operating characteristic) curve analysis. The area under the curve (AUC), 95% confidence interval, optimal cut-off value, sensitivity, specificity, Youden index, and p-values were calculated. Since PNX-14 levels were inversely related to mortality in the ROC analysis, the analysis was performed with the reversed direction. Comparison of ROC curves for PNX-14 versus procalcitonin and CRP was conducted using the DeLong test.

To identify variables linked to mortality, univariate logistic regression analysis was conducted. Variables that proved significant were included in the multivariate logistic regression model to determine independent risk factors. The Backward-Wald method was employed for variable selection. Multicollinearity among independent variables was evaluated using the variance inflation factor (VIF) and tolerance values; VIF less than 5 and tolerance values between 0.40 and 0.80 were considered acceptable. The relationships between PNX, inflammatory biomarkers, and clinical severity scores were analyzed using Pearson or Spearman correlation tests, depending on the distribution of the variables, with correlation coefficients (r) and p-values reported. In all analyses, a p-value less than 0.05 was regarded as statistically significant.

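### ICU length of stay has no assigned method and no rule for stays ended by death, so an association with PNX-14 cannot be read as recovery

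*Combined protocol and SAP*

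**What the plan says.** All references are to the combined protocol and SAP.

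- **End points.** The secondary relationships with PNX-14 include "requirements for mechanical ventilation or renal replacement therapy, and ICU length of stay in patients with sepsis". There is no restriction by vital status. The primary endpoint concerns the same marker: "Primary endpoint: the relationship between PNX14 levels and in-hospital mortality in patients with sepsis or septic shock".
- **Statistical Analysis, correlations.** "The relationships between PNX, inflammatory biomarkers, and clinical severity scores were analyzed using Pearson or Spearman correlation tests". Length of stay is neither a biomarker nor a severity score, so this sentence does not cover it. The section also gives t-tests and Mann–Whitney tests for comparing groups. No sentence says which method applies to length of stay.
- **Statistical Analysis, direction.** "Since PNX-14 levels were inversely related to mortality in the ROC analysis, the analysis was performed with the reversed direction".
- **Statistical Analysis, deaths in the cohort.** The expression values "were compared between two groups (Dead and Survived", so patients who died are analysed. The number of deaths is not given.
- **Study Design and Patients.** The exclusions cover "patients who were discharged/transferred or died within 72 hours after being diagnosed with sepsis". Later deaths remain.

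The plan contains no competing-risk or cause-specific model, no composite that ranks death, and no other rule for a stay that ends in death.

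**The concern.** An ICU stay ends in one of two opposite ways. A short stay may mean quick recovery or early death. When the marker has nothing to do with death, this mostly adds noise. Here the study's own hypothesis and its reported direction put deaths at the low end of PNX-14, so stays cut short by death should gather there too.

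Two errors then become possible if length of stay is taken as a measure of recovery. Higher PNX-14 may appear to go with longer stay only because patients with low values die sooner. Or slower recovery at low PNX-14 may be cancelled by earlier deaths, so that the correlation sits near zero. Neither a single correlation nor a rank comparison of stay between PNX-14 groups can tell these situations apart. At stake is the interpretation of one secondary endpoint.

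**Working it through.** **Inputs from the documents.** N = 77; significance at 0.05 (taken as two-sided, since the plan does not say); PNX-14 inversely related to death; exits within 72 hours of diagnosis removed. The plan gives no figure for length of stay, so there is none to reproduce. It also gives no mortality, hazard ratio or distribution of stay, so everything below on those is assumed.

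**Step 1: the mechanism in closed form.** Let x be standardised PNX-14, with constant hazards of death h_d(x) and live discharge h_r(x) after day 3. Time to exit then has rate h_d + h_r, so

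- mean further stay = 1 / (h_d + h_r)
- probability that the exit is a death = h_d / (h_d + h_r)

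Take both hazards as 1/14 per day at x = 0.

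*Case (a): PNX-14 affects death only, hazard ratio 0.5 per SD higher.*

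- x = −1: 1 / (2/14 + 1/14) = 14/3 = 4.67 days; death probability 2/3 = 67%
- x = +1: 1 / (0.5/14 + 1/14) = 14/1.5 = 9.33 days; death probability 0.5/1.5 = 33%

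Mean further stay doubles although PNX-14 has no effect on the rate of live discharge.

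*Case (b): higher PNX-14 lowers death (0.6 per SD) and speeds discharge (1.65 per SD).*

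- x = −1: 14 / (1/0.6 + 1/1.65) = 14/2.273 = 6.16 days
- x = +1: 14 / (0.6 + 1.65) = 14/2.25 = 6.22 days

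Mean stay is almost equal, although the discharge hazard differs by a factor of 1.65² = 2.72.

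*Survivors only.* With constant hazards, time to exit is independent of the type of exit. Survivors at a given x therefore have the same mean stay, 1 / (h_d + h_r), and the distortion in case (a) persists among them.

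**Step 2: simulation.** N = 77, 5,000 cohorts per scenario, stay = 3 days plus the earlier of death and discharge, Spearman at two-sided 0.05. Hazard ratios are per SD higher PNX-14.

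| Death HR | Discharge HR | Deaths | Mean rho, all | Significant, all | Mean rho, survivors | Significant, survivors |
|---|---|---|---|---|---|---|
| 1 | 1 | 50% | 0.00 | 5% | 0.00 | 5% |
| 0.5 | 1 | 35% | +0.19 | 39% | +0.16 | 22% |
| 0.5 | 1 | 50% | +0.28 | 69% | +0.24 | 31% |
| 0.5 | 1 | 63% | +0.34 | 86% | +0.29 | 34% |
| 0.6 | 1.65 | 50% | 0.00 | 5% | −0.06 | 7% |
| 0.6 | 1.65 | 36% | −0.11 | 16% | −0.15 | 18% |

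The first row shows that the test is calibrated when PNX-14 affects neither hazard.

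**Step 3: other assumptions and the alternative method.** Further runs at N = 77 removed exits before 72 hours. Death hazard ratios are now per SD *lower* PNX-14, with no effect on live discharge unless stated.

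- HR 2.2, about 39–44% deaths: Spearman significant in 55–63%; a cause-specific Cox model for live discharge in about 6%.
- HR 1.6–2.2, about 21% deaths: Spearman significant in 12–23%.
- HR 1.3: Spearman significant in 5–15%.
- Mann–Whitney comparison of stay between high and low PNX-14 halves: significant in 21–45%.
- HR 2.2 for death with slower discharge (HR 0.61): Spearman significant in 6–8%; cause-specific Cox in 76–79%.

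**The case against.** **The plan does not prescribe a correlation for length of stay.** This stands. A reader might infer one, because Pearson or Spearman is the only method named for relating PNX to other continuous measures. But that sentence covers biomarkers and severity scores only, and the End points section uses the word correlation for CRP, procalcitonin and the cytokines. A comparison of stay across a PNX-14 cut-off is equally open. The supported statement is that no method is assigned and that none of those listed handles death. The Mann–Whitney runs show that the problem does not depend on the choice.

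**A link with length of stay need not be false.** This also stands. In case (a), patients with low PNX-14 really do leave the ICU sooner. As a statement about bed occupancy the association is true; it misleads only when read as recovery. The plan does not say which is meant.

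**The size is assumed.** Correct. A reader might take the largest percentages as a property of this study, but the documents give no deaths or hazards to support that. At HR 1.3 the excess is small. Cancellation needs a near balance: with HR 2.2 for death and 0.61 for discharge per SD lower PNX-14, at about 24% mortality, rho was −0.15 and significant in 27%.

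**The simulations favour the Cox model.** In part. The data were generated with proportional cause-specific hazards. Adding unmeasured severity that doubled the death hazard and halved the discharge hazard raised the Cox model's false-positive rate to 9–11%, against 51–59% for Spearman. The advantage remains, but rejection near 5% is not guaranteed.

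**The endpoint is secondary.** Agreed. Nothing here touches the mortality comparison, the ROC analysis or the logistic regression.

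**Conclusion.** The point holds in this form: ICU length of stay is a listed endpoint without an assigned method or a rule for death, and each listed method that could be applied would mix earlier death with earlier recovery. The mechanism needs only that death ends the stay and that PNX-14 is related to death; the plan reports the second itself. Restricting to survivors does not fully cure it, because survival is itself related to the marker.

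Neither size nor sign can be derived from the documents. Under the assumed hazards, with no effect on live discharge, significance ranged from about 5–15% at HR 1.3 per SD to about 63% at HR 2.2 with about 44% deaths, and it was higher still when more deaths were assumed. With opposing effects on death and discharge, a real link could vanish. The documents do not support saying that a wrong analysis was specified, that a length-of-stay result has been misread, or that the primary conclusion is at risk. The change should be made, but it concerns one secondary endpoint.

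**What to change.** 1. State what the endpoint is meant to measure: recovery or bed occupancy.
2. For recovery, analyse time to live ICU discharge with ICU death as a competing event. Fit cause-specific Cox models on continuous PNX-14, one for live discharge and one for ICU death, and report both. Show cumulative incidence of each by PNX-14 group.
3. Use ICU exit date and ICU exit status. In-hospital death will not serve, because a patient may leave the ICU alive and die later.
4. Respect the 72-hour exclusion. It runs from sepsis diagnosis, not from ICU admission, so start follow-up, or use delayed entry, at 72 hours after diagnosis.
5. Label any raw length-of-stay correlation or group comparison as descriptive of bed occupancy, and any survivors-only version as descriptive too.

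The cost is some SAP wording and two Cox models, with no new patients or samples. The result becomes a hazard ratio instead of an r, and proportional hazards must be checked. The data items listed under Collection of Blood Samples and Data do not include ICU exit date or status, so these must be taken from the record. The analysis section is written in the past tense; if the analysis is already done, the same changes apply to the report.

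### The required sample of 64 is the per-group number for d = 0.5; the total is at least 128, so 77 patients do not meet it

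*Combined protocol and SAP*

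**What the plan says.** The sample-size justification is two sentences at the start of the Statistical Analysis section. It says "Before the study, calculations were conducted using G*Power 3.1 with 80% power", with alpha 0.05 and a medium standardised effect of d = 0.5, "indicating that at least 64 patients were needed. This requirement was met by including 77 patients in the study". It gives no test, sidedness, group ratio or allowance for loss, and nothing in the document says that 64 is a number per group.

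The comparison it served has to be read from elsewhere:

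- The End points section gives "Primary endpoint: the relationship between PNX14 levels and in-hospital mortality in patients with sepsis or septic shock".
- The Statistical Analysis section says "Group comparisons between developing and non-developing patients were conducted with the independent samples t-test", with the Mann–Whitney U test for non-normal data.
- For the qPCR values in the dead and the survivors, it says "Therefore, the differences between groups were analyzed using the Welch independent samples t-test".
- The significance rule is "In all analyses, a p-value less than 0.05 was regarded as statistically significant", again without sidedness.

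**The concern.** With d = 0.5, 80% power and a two-sided 5% level, 64 is the familiar per-group size for an independent-samples t-test. Here it is compared directly with the whole cohort of 77, so the requirement appears to have been halved.

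These sentences are the only justification of the study's size. If the figure is wrong, readers will credit the study with 80% power for a medium effect that it did not have. The damage is smaller for the primary endpoint, because the document already reports that PNX-14 runs inversely to mortality. It is greater for the two-group secondary comparisons (septic shock, mechanical ventilation, renal replacement therapy), where a non-significant result could pass as adequately powered evidence of no association.

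**Working it through.** **Inputs from the Statistical Analysis section:** power 0.80, alpha 0.05, d = 0.5, stated requirement 64, included 77.

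**Assumptions:** independent-samples t-test with equal variances; two-sided first, then one-sided; group sizes set by mortality, which the document does not give.

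**Formula.** Power comes from the noncentral t distribution with noncentrality λ = d × √(n₁n₂ / (n₁ + n₂)) and n₁ + n₂ − 2 degrees of freedom.

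**Step 1: reproduce 64.** The normal approximation per group is 2 × (1.960 + 0.842)² / 0.5² = 62.8, so 63. The exact t calculation gives 63.77, so 64:

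- 63 per group: power 0.795.
- 64 per group: λ = 0.5 × √(64 × 64 / 128) = 2.828, 126 df, critical value 1.979, power 0.801.

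The plan's figure is reproduced exactly as a per-group number, which makes the total 2 × 64 = 128.

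**Step 2: try 64 as a total.** With 32 per group, λ = 0.5 × √(32 × 32 / 64) = 2.0 and power is 0.504.

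**Step 3: look for another t-test with a total of 64 at d = 0.5.**

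| Test | Total needed |
|---|---|
| Two groups, two-sided | 128 (64 per group) |
| Two groups, one-sided | 102 (51 per group, power 0.806) |
| Paired or one-sample, two-sided | 34 |
| Paired or one-sample, one-sided | 27 |

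None gives 64. A paired design is also ruled out, because blood was taken once per patient and the comparison is between different patients. The Mann–Whitney test does not lower the requirement: for normal data its efficiency is 3/π, so 63.77 / 0.955 = 66.8, or 67 per group and 134 in total.

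**Step 4: power with 77 patients at d = 0.5.** For the most even split, λ = 0.5 × √(38 × 39 / 77) = 2.194 with 75 df. All splits are assumed.

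| Smaller / larger group | Power, two-sided | Power, one-sided | d for 80% power, two-sided |
|---|---|---|---|
| 38 / 39 | 0.581 | 0.702 | 0.65 |
| 23 / 54 | 0.509 | 0.635 | 0.71 |
| 15 / 62 | 0.404 | 0.531 | 0.82 |

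**Step 5: two-sided totals for unequal groups at d = 0.5.** About 133 are needed at 40% mortality, 152 at 30% and 198 at 20%. Rounding conventions move these by about one patient.

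**The case against.** The strongest reply is that the origin of 64 is reconstructed, since the document names neither test nor sidedness. One calculation does give 64 in total: a one-sided point-biserial correlation between a continuous marker and a binary outcome, with r = 0.3 (power 0.8005). If that was run, the mistake would be the label d = 0.5, and 77 would be enough. It is a possible explanation but a weak one. It contradicts the printed effect size, and r = 0.3 appears nowhere in the document. The correlation equivalent to d = 0.5 in equal groups is 0.5 / √(0.5² + 4) = 0.243, which is smaller and needs about twice as many patients. What stands is that the correction should be filled in from the saved G*Power output.

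A second reply is that little follows: the data are collected, some results are already in the text, and no estimate or test changes. That is largely fair. It is also right that the d = 0.5 calculation never sized the correlations with severity scores and cytokines, the ROC analysis or the logistic model, so it says nothing about their power. The plan nowhere says that it will read non-significance as no association. None of this makes the sample-size statement correct.

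**Conclusion.** The concern holds. On the plan's own inputs, any two-group t-test needs more than 77 patients. The shortfall is at least 128 − 77 = 51 two-sided, or 102 − 77 = 25 one-sided with equal groups, and it grows as the split becomes less even. Available power for d = 0.5 is at most about 58% two-sided or 70% one-sided. The smallest effect detectable with 80% power is d of about 0.65 two-sided (0.57 one-sided) at the best split.

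The conclusion rests on one inference: that the calculation served a comparison of two independent groups. The use of d, the primary endpoint, the planned tests and the exact match of 64 to the per-group size all support it. It does not depend on sidedness or on the unknown mortality, since every split of 77 falls below 80% power. The statement must be corrected because it is wrong as written; the planned analyses themselves are unaffected.

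**What to change.** Retrieve the saved G*Power output and report its test, sidedness, effect measure and group ratio. Keep the record of the calculation and correct it openly. If the output confirms a two-sided independent-samples t-test, wording such as this would do:

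> The calculation made before the study (G*Power 3.1; 80% power, alpha 0.05, d = 0.5; two-sided independent-samples t-test) gave 64 patients per group, that is 128 in total with equal groups and more with unequal groups. The 77 patients included fell short of this. With the observed [n] deaths and [n] survivors, the study has 80% power for d of [value] or larger.

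Fill the brackets from the actual split, which the investigators hold. If the output shows a different test or effect measure, report that and correct the d = 0.5 label. Add a sentence saying that non-significant results, mainly among the secondary associations, will be interpreted by their confidence intervals and not as evidence of no association.

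The cost is a few sentences and one recalculation. No patients are added and no analysis changes; the only downside is a less favourable statement of power.

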At the time of ICU admission, parameters such as age, gender, body mass index (BMI), comorbidities, infection focus, complete blood count, CRP, procalcitonin, Acute Physiology and Chronic Health Evaluation (APACHE) II score, Sequential Organ Failure Assessment (SOFA) score, vasopressor requirement, mechanical ventilation need, and renal replacement therapy requirement were recorded. On the first day of hospitalization, 3 mL of blood was routinely collected from patients for biochemical analysis. The levels of IL-6, TNF- α , IL-1 β , IL-10, and PNX14 were measured using real-time PCR, while serum levels were determined using ELISA. Blood samples were collected once at ICU admission to assess baseline PNX-14 levels for early prognostic evaluation.

RNA Isolation

Total RNA was isolated from peripheral blood samples using the NucleoSpin RNA Blood kit (Macherey-Nagel, Germany) according to the manufacturer's instructions. RNA concentration and purity were assessed using a Qubit 2.0 Fluorometer (Thermo Fisher Scientific).

RNA Quality Control – Agarose Gel Electrophoresis

RNA integrity was assessed by agarose gel electrophoresis. Briefly, RNA samples were separated on a 1% agarose gel and visualized using a gel documentation system to confirm RNA integrity, according to standard laboratory procedures.

RNA Concentration Measurement – Qubit Fluorometric Method

RNA concentration and quality were assessed using a Qubit 2.0 Fluorometer (Thermo Fisher Scientific, USA) and the Qubit RNA HS Assay Kit, following the manufacturer's recommended protocol.

cDNA Synthesis

Complementary DNA (cDNA) was synthesized from total RNA using the High-Capacity cDNA Reverse Transcription Kit (Thermo Fisher Scientific, USA) as per the manufacturer's protocol.

Quantitative Real-Time PCR (qRT-PCR)

Quantitative real-time PCR analysis was performed using SYBR Green Master Mix (AMPLIFYME SYBR Universal Mix) on an Applied Biosystems StepOnePlus system. GAPDH was used as the reference gene due to its reported expression stability in peripheral blood samples under inflammatory conditions. Relative gene expression was calculated using the $2^{-\Delta\Delta Ct}$ method, with GAPDH as the internal control. In the absence of a healthy control group, the survivor group was used as the calibrator for relative expression analysis. Primer sequences are listed in Table 1.

Table 1. Primers used in the study

	Forward Primer	Reverse Primer

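### The adjusted PNX-14 odds ratio comes from an uncapped, p-value-selected maximum-likelihood model in 77 patients and, if the effect is real, is on average too far from 1

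*Combined protocol and SAP*

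**What the plan says.** The Statistical Analysis section screens variables by univariate logistic regression on mortality and then says: "Variables that proved significant were included in the multivariate logistic regression model to determine independent risk factors". The only threshold given is the general one: "In all analyses, a p-value less than 0.05 was regarded as statistically significant". Backward-Wald then reduces the model; its removal threshold is not stated. The one model check is on VIF and tolerance, which concerns collinearity and not the number of outcomes per parameter. No penalised or bias-reduced fit is mentioned, so ordinary maximum likelihood (ML) is taken as the method.

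The list of variables screened is not given. The section on blood samples and data records a wide set: "At the time of ICU admission, parameters such as age, gender, body mass index (BMI), comorbidities, infection focus, complete blood count, CRP, procalcitonin", followed by severity scores and organ-support needs, and then four cytokines and PNX-14. On numbers, the plan says: "This requirement was met by including 77 patients in the study". Deaths are not reported. The primary endpoint is "the relationship between PNX14 levels and in-hospital mortality in patients with sepsis or septic shock".

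**The concern.** Two features push the adjusted odds ratio the same way. First, ML logistic estimates are biased away from the null when there are few outcomes per fitted parameter, and here the number of fitted parameters follows from how many screens happen to be significant. Second, PNX-14 appears in the final model only if its estimate is strong enough to pass both the screen and Backward-Wald, so the estimates that get reported are preferentially the large ones.

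This is the only planned analysis that adjusts PNX-14 for other variables. Any statement that PNX-14 is an independent risk factor rests on it, and an overstated odds ratio would be carried into that statement.

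**Working it through.** **The plan's own figure.** There is none for the regression. The only design figure, "indicating that at least 64 patients were needed", comes from d = 0.5, 80% power and α = 0.05. For two independent groups, two-sided, 2 × (1.96 + 0.842)² / 0.5² = 62.8, or 64 with the t correction. That is per group, 128 in total. This is a separate sample-size matter and nothing below depends on it.

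**Outcomes against candidates.**
- Clinical items named: 13, counting comorbidities, infection focus and blood count as one each. Adding four cytokines and PNX-14 gives 18. That all 18 were screened is an assumption.
- The smaller outcome class is at most 38 (77 / 2, rounded down), so there are at most 38 / 18 = 2.1 outcomes per candidate.
- Bias depends on fitted parameters, not candidates. With 8 fitted: 15 / 8 = 1.9 outcomes per variable at 15 deaths, 31 / 8 = 3.9 at 31 deaths, and 38 / 8 = 4.8 at best.

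**ML bias alone, model fixed.** Simulated studies of 77 patients; normal predictors correlated 0.3 in absolute value; true PNX-14 odds ratio 0.50 per SD; up to four other predictors with log odds ratio 0.4; mortality 20% to 60% (assumed); 800 runs per setting. Odds ratios are geometric means.

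| Predictors fitted | Inflation of mean ML log-OR | ML odds ratio | Firth odds ratio |
|---|---|---|---|
| 3 | 7% to 11% | 0.464 to 0.477 | 0.496 to 0.507 |
| 5 | 13% to 22% | 0.429 to 0.458 | 0.495 to 0.505 |
| 8 | 20% to 31% | 0.404 to 0.435 | 0.498 to 0.504 |
| 12 | 38% to 67% | 0.313 to 0.385 | 0.480 to 0.499 |

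The 67% arises at 20% mortality, where 5% of the 12-predictor fits were separated or nearly so; at 30% to 60% mortality the range is 38% to 41%. Medians are lower than means (4% to 8% with three predictors).

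A second set-up (true log-OR −0.80, one other real predictor, the rest null, about 21 or 30 deaths) agrees:
- 3 predictors: −0.87 to −0.90, and 0.87 / 0.80 = 1.09, 0.90 / 0.80 = 1.125.
- 9 predictors: −0.98 to −1.00, 22% to 25% too large.
- 12 predictors: −1.01 to −1.10, 26% to 38% too large.
- Firth: −0.78 to −0.83 throughout.

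**The planned procedure.** 18 candidates, univariate p < 0.05, then Backward-Wald (removal at p > 0.10 assumed), true log-OR −0.69, four other real predictors, mortality 20% to 50%. A median of 9 to 12 variables entered and about 3 remained. PNX-14 was retained in 56% to 69% of runs; when retained, its mean log-OR was 50% to 72% too large.

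A further set of runs of the same rule separates the two sources:
- ML on the selected model: −1.06 to −1.13 (1.06 / 0.69 = 1.54; 1.13 / 0.69 = 1.64).
- Firth on the same selected model: −0.94 to −0.98 (0.94 / 0.69 = 1.36; 0.98 / 0.69 = 1.42).
- Firth on a small covariate set fixed without reference to the screens: −0.66 to −0.70, essentially unbiased.

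Pairing the ends of these ranges, the excess falls from 0.37 to 0.25, or from 0.44 to 0.29. About two-thirds of the overstatement is therefore left after Firth and is due to selection.

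**The case against.** Several counter-arguments are sound.

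- **Large models may not arise.** The bias for 9 to 12 predictors belongs to models in which all are fitted together, whereas the plan ends with a reduced model. Where only two of 12 candidates have real effects, the planned rule admitted a median of one variable, six or more entered in under 1% of runs, and the retained PNX-14 log-OR was only 5% to 12% too large. A reader might infer that the reported odds ratio is overstated by a quarter or a third through ML bias alone. The documents do not support that, because they do not say how many variables entered or remained.
- **The ML part is modest.** About 10% of a log-OR of 0.80 is 0.08, against a sampling SD of 0.34 to 0.38 with three predictors. This stands. The larger overstatement requires selection as well.
- **Firth is not enough.** Applied to the selected model it still leaves the estimate roughly a third to a half too large. This stands, and it is why the selection step must change too.
- **Model size is not wholly detached from deaths.** A p < 0.05 screen admits fewer variables when events are fewer: a median of 12 at about 38 deaths and 9 at about 13. What is missing is an explicit limit.
- **The model is not named as the primary analysis.** That is correct, and it limits the consequence to claims of independent effect.

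None of this supplies a cap, a fixed covariate set or bias reduction, which the plan lacks.

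**Conclusion.** The point holds as an average tendency and merits a change, though it does not invalidate the study. If PNX-14 truly matters, the planned procedure yields an adjusted odds ratio that is on average too extreme: about 7% to 12% on the log scale from ML bias in a model of about three variables, about 20% to 40% or more with 9 to 12 fitted together, and a further amount from conditioning on retention.

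These sizes depend on the assumed number of deaths, candidate list, correlations, true effects and removal threshold, none of which the documents give.

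Two stronger readings should be resisted. It does not follow that the odds ratio in this particular dataset is overstated, since a single estimate can fall on either side. Nor does it follow that PNX-14 has no independent effect. If it truly has none, ML bias has nothing to inflate and only selection can mislead: PNX-14 was then retained in 5% to 7% of runs, with a mean odds ratio of about 0.45 to 0.53.

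**What to change.** For the adjusted PNX-14 odds ratio:

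- Replace the univariate screen and Backward-Wald with a small covariate set chosen on clinical grounds without reference to the p-values, with PNX-14 always in the model.
- Limit the number of parameters by the smaller of deaths and survivors, and state the limit. One per 10 is a rule of thumb, given here as illustration: 1 parameter at 15 deaths, 2 at 23, and 3 at 31, 38 or 46 deaths (46 deaths leave 31 survivors). PNX-14 counts as one of them.
- Fit by Firth's penalised likelihood with profile-likelihood confidence intervals.
- Report deaths, the variables screened and the number entered. Present the screened Backward-Wald model as exploratory.
- Label this as a revised analysis. The plan already reports the number included and test results, so it cannot be called pre-specified.

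The cost is SAP wording and a short re-fit of existing data in R or an SPSS extension. Fewer covariates are adjusted for, which leaves more room for residual confounding, and the odds ratio is likely to be less extreme.
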